Statistical Analysis Plan (SAP)

Study Title	Heart rate and Breathing Effects on Attention and Memory (HeartBEAM)
Principal Investigator	[name] Professor of Gerontology, Psychology and Biomedical Engineering University of Southern California Los Angeles, California, USA
Protocol identification number	UP-21-00357
ClinicalTrials.gov identifier	NCT05602220
Author	[name] Research Associate [name] of Southern California Los Angeles, California, USA
Version	Draft 0.1
Date	09/02/2025

1. Objectives and hypotheses

In our previous HRV-ER trial (NCT03458910), four weeks of daily slow-paced breathing designed to enhance parasympathetic activity reduced plasma A β levels in both younger and older adults. The current study aimed to extend those findings in adults aged 50 to 70 years using a 10-week intervention with three assessment time points. Secondary objectives included examining the effects of slow-paced breathing on brain structure (i.e., perivascular space and hippocampal volumes) and cognitive performance. We hypothesized that the 10-week slow-paced breathing intervention would reduce plasma A β levels and lead to improvements in brain structure and cognitive performance.

2. Sample Size & Power consideration

For plasma A β , we estimated reliability using correlations between pre- and post-intervention time points in the HRV-ER trial. Effect sizes were derived from the pre-post difference in the HRV-ER older adult Osc+ (slow-paced breathing) group. We powered the study to detect small-to-medium effect sizes ($f = .2$) with a .7 correlation among repeated measures and aimed for 95% power at $\alpha = .05$. Based on these parameters, a total sample size of $N = 42$ (with three assessments) was required. Sixty-two participants (31 in each condition) ultimately completed the study.

3. Outcome Measures and Analyses

We examined condition differences (slow-paced breathing vs. random-paced breathing) in intervention-related change in the following outcome measures. The average time between pre and post intervention assessment was 10 weeks.

Primary outcome measures

- **Change in plasma amyloid beta levels:** We computed an aggregate score based on plasma A β 40 and A β 42 levels (pg/mL), calculated as the average of their Z-scores. Higher values on this composite measure are associated with greater risk of Alzheimer's disease. This score was compared across three time points: Week 2 (pre-intervention), Week 7 (mid-intervention), and Week 12 (post-intervention). We conducted a time (Week 2, 7, 12) \times condition ANOVA to test for a time \times condition interaction in plasma A β levels, assessing group differences in change over time.
- **Change in plasma Ab42/40 ratio:** The plasma A β 42/40 ratio was calculated by dividing the plasma A β 42 concentration (pg/mL) by the plasma A β 40 concentration (pg/mL) at each time point. We conducted a time (Week 2, 7, 12) \times condition ANOVA to test for an interaction effect, using plasma A β 42/40 ratio scores as the dependent variable to assess group differences over time.

Secondary outcome measures

- **Change in brain perivascular space (pvs) volume:** PVS volume was defined as the percentage of PVS volume relative to white matter volume in the centrum semiovale, our main region of interest. To examine condition differences in changes over time, we conducted a time (Week 2, 7, 12) \times condition ANOVA to test for an interaction effect.

- **Change in hippocampal volume:** We tested whether there were condition differences in changes in hippocampal volume. We performed a two-way mixed ANCOVA on hippocampal volume, with condition (slow-paced vs. random-paced) as the between-subjects factor and time point (Week 2, 7, 12) as the within-subjects factor, controlling for intracranial volume as a covariate.
- **Brain training performance on 12 Lumosity games during the breathing intervention (controlling for brain training performance pre intervention):** Increments in game play performance over the course of the intervention were captured on latent level, with all games contributing to the latent variable. To evaluate longitudinal changes in cognitive performance during the intervention, we fitted a linear mixed-effects model to participants' latent performance scores across the 10 time bins. We examined condition differences in performance changes over time.

Other pre-specified outcome measures

- Change in plasma pTau-181/tau ratio:
- Change in urine Ab42

Safety outcomes

Six non-serious adverse events were reported and subsequently resolved.

4. Populations and subgroups to be analyzed

Population analyzed is composed by all randomization subjects who completed assessments and whose data quality was sufficient for data analysis.

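### Does taking the effect size from a one-arm pre-post change leave the time × condition test underpowered?

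*SAP*

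**What the plan says.** SAP Section 2 gives the source of the effect size: "Effect sizes were derived from the pre-post difference in the HRV-ER older adult Osc+ (slow-paced breathing) group". It then states the target, "We powered the study to detect small-to-medium effect sizes", with f = .2, "with a .7 correlation among repeated measures", 95% power and α = .05. The result is N = 42 with three assessments, and 62 participants (31 per arm) completed.

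SAP Section 3 opens with the comparison of interest: "We examined condition differences (slow-paced breathing vs. random-paced breathing) in intervention-related change". Both primary outcomes use a time (Week 2, 7, 12) × condition ANOVA. For the composite the test is of the "interaction in plasma A β levels, assessing group differences in change over time"; for the 42/40 ratio the model takes "ratio scores as the dependent variable to assess group differences over time".

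Section 4 restricts the analysis to randomised participants "who completed assessments and whose data quality was sufficient for data analysis", so the number analysed may be below 62.

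The Protocol has no sample size section. Its account of the home intervention (Week 2-12) describes an active comparator: random-paced breathing with biofeedback that rewards less heart rate oscillation, the reverse of the slow-paced arm's goal.

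**The concern.** A change within one arm does not determine an interaction. The interaction depends on the difference between the two arms' changes, so the comparator's change is needed as well. Section 2 gives no figure for the earlier arm's change, makes no stated assumption about the random-paced arm, and does not say whether f = .2 stands for time or for time × condition.

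If a one-arm f had been entered directly as the interaction f, the calculation would hold only if the comparator moved equally far in the opposite direction. With a flat comparator the interaction f would be half as large. The 95% figure would then overstate the power of both primary tests, and a reader might rely on it to treat a non-significant interaction as evidence of no effect.

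**Working it through.** **Inputs (SAP Section 2).** f = .2, r = .7, α = .05, m = 3 assessments, N = 42 required, 62 completers. Two arms (Section 3). Sphericity is assumed.

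**Formula.** For the interaction in a repeated-measures ANOVA, power comes from the noncentral F distribution with λ = f² × N × m / (1 − r), df1 = (2 − 1)(3 − 1) = 2 and df2 = 2(N − 2).

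**Step 1: reproduce the stated N, with f = .2 as the interaction effect.**

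| N | λ | df2 | Power |
|---|---|---|---|
| 40 | .04 × 40 × 3 / .3 = 16.0 | 76 | 94.9% |
| 42 | .04 × 42 × 3 / .3 = 16.8 | 80 | 95.9% |
| 62 | .04 × 62 × 3 / .3 = 24.8 | 120 | 99.6% |

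The smallest even N that reaches 95% is 42, as stated.

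**Step 2: does N = 42 reveal which effect was entered?** No. With two arms and three visits, the main effect of time has the same λ and the same degrees of freedom, so it also gives 95.9% at 42. The choice of reading has to come from the text.

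**Step 3: what if f = .2 were the slow-paced arm's own three-visit effect?** This is an assumption that the SAP does not make. Let the comparator move c times as far as the slow-paced arm, with c > 0 meaning the same direction. Each arm departs from the average time course by half the difference between them, so interaction f = .2 × (1 − c) / 2.

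| Comparator | Interaction f | Power at 42 | Power at 62 |
|---|---|---|---|
| A quarter as far, same direction (c = .25) | .075 | 25% | 36% |
| Flat (c = 0) | .10 | 42% | 59% |
| Half as far, opposite direction (c = −.5) | .15 | 78% | 92% |
| Mirror image (c = −1) | .20 | 95.9% | 99.6% |

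A simulation of the mixed ANOVA with 31 per arm gave the same results at 62 to within 1 percentage point.

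**Step 4: margin on the interaction reading.** The number analysed could fall from 62 to 42, a loss of 20, before power dropped to the planned level. If sphericity failed with ε = .75 (an assumption), the required N would be 50, still below 62.

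**Step 5: which reading does the text support?** Section 2 presents f = .2 as a small-to-medium effect to be detected, which reads as a rounded target. It does not equate .2 with the earlier arm's change. Section 3 defines the question as a difference between conditions and tests it by the interaction. Taken together, the two sections support f = .2 as the interaction effect, and Step 1 then shows no shortfall.

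**The case for a change.** The strongest case for a change is that 95% is the only power figure in the SAP, and that its key input cannot be traced. N = 42 fits a time effect as well as an interaction. The comparator is active, and the documents do not say how its plasma amyloid should move, so movement in the same direction, no movement and opposite movement all remain open. The SAP is marked Draft 0.1, so one sentence naming the effect and its derivation would cost little. A 2-df interaction test also shows neither the size nor the direction of a difference, so a between-arm difference in Week 2 to Week 12 change with its 95% interval would tell the reader more than the power figure.

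The omission stands: the derivation is not given. The step from omission to defect does not. The figures of 36% and 59% need two assumptions together, that .2 is the one-arm effect and that the comparator follows a particular path, and the SAP states neither. The opposing biofeedback goals do not prove opposite amyloid changes, but they are a reason not to treat the flat or same-direction cases as the expected ones. The SAP uses the 95% as a planning aim tied to f = .2, and nowhere says that a null result will be read from it. Reporting the difference with its interval is good practice, but it corrects no rule in the plan.

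**Conclusion.** No change to the plan is needed. Section 2 omits one line of derivation, but its arithmetic is right: for an interaction of f = .2 with r = .7 and sphericity, power is 95.9% at 42 and 99.6% at 62. Lower figures, such as 59% with a flat comparator, are conditional illustrations and show no error in the stated sample size.

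The trial has finished with 20 more completers than the calculation required. Filling in the derivation would leave N, the data and the two primary tests as they are, and conclusions drawn from those tests do not depend on it.

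Two limits apply. The reassurance rests on reading f = .2 as the interaction effect, which the text supports but does not state. And Section 2 gives its reliability estimate for plasma amyloid, with no separate correlation for the 42/40 ratio, so the power figures carry over to the ratio only if its correlation is similar.

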Study Protocol

Title: Heart rate and Breathing Effects on Attention and Memory (HeartBEAM)

NCT number: NCT05602220

IRB approval date: 5/15/2023

Uploaded date: 12/08/2025

Research Background

As we age, the parasympathetic system declines as the sympathetic system becomes hyperactive. In our previous clinical trial (Nashiro et al., 2023; Yoo et al., 2023), we found that increasing parasympathetic activity through daily practice of slow-paced breathing significantly decreased plasma amyloid- β (A β) in healthy younger and older adults (Min et al., 2023). In healthy adults, higher plasma A β is associated with greater risk of Alzheimer's disease (AD). Our primary goal of the current trial is to extend our initial findings regarding effects of slow-paced breathing on A β . Our secondary objectives are to examine the effects of daily slow-paced breathing on brain structure and the rate of learning.

Research Objectives

The aim of the study is to examine how daily paced breathing affects plasma A β levels and the rate of learning in older adults. Healthy adults aged 50-70 who meet all eligibility criteria will be invited to this study. Participants will be randomly assigned to one of the two conditions: 1) Daily memory and attention training followed by a paced breathing protocol designed to increase relaxation or 2) Daily memory and attention training followed by a paced breathing protocol to increase alertness. Participants will be asked to complete pre and post intervention cognitive testing online, engage in 10 weeks of daily brain training (starting Week 2) and 9 weeks of paced breathing (starting Week 3) at home. They will also be asked to come in for lab visits on Weeks 2, 7 and 12 to provide blood and urine samples to assess amyloid beta levels and to complete magnetic resonance imaging scans to assess perivascular space volume.

Methods and Design

Overview of the study

Timeline	Lab Visit	Home Tasks
Week 1		online consent, home cognitive testing
Week 2	(Visit 1) EEG tasks, questionnaires (Visit 2) MRI, blood & urine samples, cognitive tasks, questionnaires, give heart rate monitoring device	(Training Week 1) cognitive training + resting pulse measures (~40 min/day)
Week 3		(Training Week 2) cognitive + breathing training (~60 min/day)
Week 4		(Training Week 3) cognitive + breathing training (~60 min/day)
Week 5		(Training Week 4) cognitive + breathing training (~60 min/day)
Week 6		(Training Week 5) cognitive + breathing training (~60 min/day)

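### The three-visit ANOVAs enter the pre-treatment Week 2 value as an outcome level and do not adjust for it: valid, but about 6–20% of the information is given up at the SAP's correlation of .7 for plausible effect patterns

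*SAP*

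**What the plan says.** SAP section 3 defines the first primary outcome as the average of the Aβ40 and Aβ42 Z-scores and says of it: "This score was compared across three time points: Week 2 (pre-intervention), Week 7 (mid-intervention), and Week 12 (post-intervention"). The test is the interaction in a time (three levels) × condition ANOVA. The second primary uses the same ANOVA with the 42/40 "ratio scores as the dependent variable to assess group differences over time". Perivascular space volume, a secondary outcome, is handled identically. No baseline covariate is named for any of the three. Hippocampal volume is analysed by a two-way mixed ANCOVA over the same three visits, "controlling for intracranial volume as a covariate". Only the Lumosity outcome names control for pre-intervention performance.

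The Protocol (Research Objectives) schedules "9 weeks of paced breathing (starting Week 3"). Under the Protocol's visit descriptions, the Week 2 blood and urine samples and MRI are taken at the visit that ends with the hand-out of the training devices. SAP section 2 sets f = .2, 95% power and α = .05 "with a .7 correlation among repeated measures", and concludes that "a total sample size of $N = 42$ (with three assessments) was required". It reports 62 completers, 31 per condition. SAP section 4 analyses randomised participants who completed assessments and whose data were of sufficient quality.

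**The concern.** One of the three outcome levels is measured before the arms are treated differently, so among all randomised participants the two arms have the same expected Week 2 value. The ANOVA makes no use of this. It fits a separate Week 2 mean for each arm and judges the effect by change, which amounts to fixing the slope on baseline at 1. With equal variances and a correlation of .7, the best slope is .7.

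Two things follow. Treatment contrasts are less precise than the same data allow. And if the arms differ by chance at Week 2, regression to the mean enters the result: the arm that starts higher tends to fall relative to the other arm with no treatment effect at all. For a trial whose hypothesis is a reduction in plasma amyloid, a slow-breathing arm that started high by chance would look better than it should, and one that started low would look worse.

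**Working it through.** **Inputs.** From SAP section 2: f = .2, r = .7, α = .05, 95% power, N = 42 required, 31 per arm completed. Assumed: equal variances (SD = 1), the same correlation between every pair of visits (the SAP gives one value), and complete data.

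**1. The SAP's own figure.** For the within–between interaction, λ = f²·N·m/(1 − r), with m = 3, df = 2 and 2(N − 2).
- N = 42: λ = .04 × 42 × 3/.3 = 16.8, power .959.
- N = 40: λ = 16.0, power .949.

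So 42 is the smallest even total, and the SAP's figure reproduces. At N = 62, λ = 24.8 and power is .9955.

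**2. Information in the two tests.** Let δ be the arm differences at Weeks 7 and 12, with zero at Week 2.
- ANOVA: Σ(δₜ − δ̄)²/(1 − r), summed over all three visits.
- Adjusted: δ′S⁻¹δ, where S is the covariance of Weeks 7 and 12 given Week 2. Its diagonal is 1 − r² = .51 and its off-diagonal is r − r² = .21. The determinant is .51² − .21² = .216.

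| Pattern (Week 7, Week 12) | ANOVA | Adjusted | Gain from adjusting | Share discarded by ANOVA |
|---|---|---|---|---|
| Equal (1, 1) | .667/.3 = 2.222 | 2/.72 = 2.778 | 25% | 20% |
| Linear (.5, 1) | .5/.3 = 1.667 | .4275/.216 = 1.979 | 19% | 16% |
| One visit (0, 1) | .667/.3 = 2.222 | .51/.216 = 2.361 | 6% | 6% |
| Opposite (1, −1) | 2/.3 = 6.667 | 1.44/.216 = 6.667 | 0% | 0% |

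Gain and loss are different scales: 2.778/2.222 = 1.25, but 1 − 2.222/2.778 = .20.

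As a cross-check on single contrasts, the Week 12 change score has variance 2(1 − r) = .60 against 1 − r² = .51 adjusted, so 15% is lost. The mean of the two post-treatment visits gives .45 against .36, so 20% is lost. Simulation at 31 per arm, which includes the cost of estimating the slope, gave losses of 14% and 19%.

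**3. Sensitivity to r.** For an equal effect the share discarded is 33% at r = .5, 20% at .7, 13% at .8 and 7% at .9.

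**4. Baseline imbalance.** Given a Week 2 difference b, the change-based estimate shifts by −(1 − r)b = −.30b. Simulation gave a slope of −.301, against −.002 for the adjusted estimate. The standard error of b is √(2/31) = .254 SD, so a one-standard-error imbalance shifts the estimate by .30 × .254 ≈ .08 SD.

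**5. Power at N = 62.** At f = .2, power is .9955 for the ANOVA, and raising λ by 6–25% takes it to .997–.999. Under the SAP's convention, an equal effect d gives f² = d²/18, so f = .2 corresponds to d = √(18 × .04) = .85 SD. The documents state no between-arm difference. Taking 0.5 SD as an assumption, f = .5/√18 = .12 (equal or one visit) or .5/√24 = .10 (linear). Simulated power, ANOVA to adjusted joint test:
- equal: .74 to about .82
- linear: .61 to about .67
- Week 12 only: .74 to about .75

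Type I error was close to .05 for both tests.

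**The case against.** The strongest reply is that a valid, amply powered method was chosen. That largely stands. The interaction test holds its type I error, and at the SAP's own effect size there is almost no power left to gain. A reader might infer that the trial is underpowered or its primary result biased. The documents support neither. The estimate is unbiased over randomisation, the .08 SD shift is conditional on an imbalance, and no observed Week 2 imbalance is reported. The power reply does depend on f = .2, which the SAP derived from the pre–post difference within the slow-breathing group of the earlier trial rather than from a difference between arms. For smaller true effects the loss is not trivial.

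The adjusted model has a cost. Its joint test with unstructured covariance has about 58 denominator df, against 2 × 60 = 120 for the ANOVA under sphericity. This offsets nearly all of the gain for an effect at Week 12 only, and at very high correlations the adjusted test can be slightly the weaker one.

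Three tempting stronger readings also fail:
- A reader might take the loss to be as much as 25%. That is the gain from adjusting; the loss for an equal effect is 20%.
- A reader might say that intracranial volume does nothing in the hippocampal test. That is so only if it is constant within a person and enters without a covariate × time term, which the SAP does not specify. Either way, it does not stand in for Week 2 hippocampal volume.
- A reader might say that randomisation guarantees equal expected baselines. It does so for everyone randomised, but SAP section 4 analyses completers with adequate data, and there equality is an assumption.

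**Conclusion.** The point holds as one of efficiency and robustness, not of validity. At r = .7, with equal variances and one common correlation, the three-visit ANOVA discards about 20%, 16% or 6% of the available information for an equal, linear or single-visit effect, and nothing for equal and opposite effects. It also leaves the estimate exposed to chance Week 2 imbalance, at −.30 SD per SD. Planned power is unaffected in practice. The benefit would be greatest for an outcome whose true correlation is below .7 and small for one near .9, which may be the case for hippocampal volume; the documents give no correlation specific to that outcome. Since the SAP already controls for pre-intervention performance in the Lumosity analysis, leaving the Week 2 value out of the primary analyses is an avoidable inconsistency that is worth correcting.

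**What to change.** For each three-visit outcome, fit a repeated-measures model of the Week 7 and Week 12 values on condition, visit, condition × visit, Week 2 value and Week 2 value × visit, with unstructured covariance. Test the condition difference at Weeks 7 and 12 jointly (2 df). Prefer this covariate form to a model that keeps Week 2 as an outcome with one common mean, because the latter imposes equal baselines on a completer set in which they are not assured. For hippocampal volume, add Week 2 hippocampal volume as a covariate. Intracranial volume may stay, but the SAP should say whether it interacts with time.

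The SAP is marked as a draft yet written in the past tense, so the ANOVAs may already have been run. Keep them reported, add the adjusted model for all four outcomes whatever it shows, and state when it was specified. If it came after the ANOVA results were seen, label it as such and do not let it silently replace the primary test.

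The cost is SAP wording and four additional models on data already collected, with the lower denominator df noted above. No new data or participants are needed.

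### Two unranked primary outcomes, each with its own ANOVA, and no success rule: if either one suffices, the false-claim rate exceeds 5% (at most 10%)

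*SAP*

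**What the plan says.** SAP section 3, under the primary outcomes, has two bullets. The first averages the Z-scores of plasma Aβ40 and Aβ42 and tests the time (Weeks 2, 7, 12) × condition interaction by ANOVA. The second, "Change in plasma Ab42/40 ratio", runs a separate ANOVA of the same form, with the "ratio scores as the dependent variable to assess group differences over time". Neither bullet is ranked above the other. Section 3 also has a secondary tier and a further pre-specified tier; the ratio is in neither.

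Section 2 "aimed for 95% power at" an alpha of .05, using f = .2 and a repeated-measures correlation of .7, and introduces that calculation as being for plasma Aβ. It adds: "Sixty-two participants (31 in each condition) ultimately completed the study". No other alpha appears. The protocol contains no analysis plan that could supply a rule. The SAP is labelled draft 0.1, dated 09/02/2025, and describes its analyses in the past tense.

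**The concern.** The rate of false primary claims depends on a decision rule that is not written down. As the plan stands, two primary interaction tests can each be read at .05, and either could be put forward as the trial's finding.

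The two outcomes can also disagree. If Aβ40 and Aβ42 fell by the same proportion, the aggregate would fall while the ratio stayed the same. The SAP does not say what the trial would then conclude. Because the text was written after participants had completed the study, a reader cannot exclude that emphasis was chosen with the results in view.

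**Working it through.** **Inputs from SAP section 2:** alpha .05, f = .2, correlation among repeated measures .7, three assessments, two arms, stated N = 42, and 62 completers (31 per arm). **Assumed, because the documents do not give it:** the correlation between the two outcomes.

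**1. The plan's own figure.** For the interaction test with sphericity, λ = N × 3 × f² / (1 − .7), with 2 and 2(N − 2) df.
- N = 40: λ = 40 × 3 × .04 / .3 = 16.0, power 94.9%.
- N = 42: λ = 16.8, power 95.9%.

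So N = 42 is reproduced as the smallest even total reaching 95%, for one test at .05.

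**2. Either outcome suffices, both null.**
- Independent tests: 1 − .95² = .0975.
- Any dependence: at most .05 + .05 = .10.
- It falls to .05 only if the two tests always reject together.

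**3. Effect of dependence.** I simulated two 2-df interaction F tests with 31 per arm, compound symmetry at .7, both outcomes null, and at least 600,000 replicates per correlation. Rates count any significant interaction, whatever its direction.

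| Assumed correlation | 0 | .3 | .5 | .7 | .9 |
|---|---|---|---|---|---|
| Either p < .05 | 9.69% (exact 9.75%) | 9.56% | 9.16% | 8.50% | 7.09% |
| Both p < .05 | 0.25% | 0.46% | 0.85% | 1.55% | 2.83% |
| Holm, any rejection | 4.94% | 4.81% | 4.71% | 4.38% | 3.63% |

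Check: the first two rows must sum to 10%, and they do within simulation error.

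**4. One outcome responds, the other is null** (200,000 replicates per correlation, 0 to .9).
- Requiring both: the null outcome leads to a false claim in 4.7% to 5.0% of replicates at f = .2, and in 3.1% to 3.4% at an assumed 0.5 SD between-arm difference in linear change.
- Holm: the null outcome is falsely rejected in 4.8% to 5.0% at f = .2, and in 3.8% to 4.1% at 0.5 SD.

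**5. Power cost with N = 62.** A linear between-arm difference of d SD by Week 12 gives f = √[(2/3)(d/4)²]. The SAP's f = .2 therefore corresponds to d = .8 / √(2/3) = 0.98 SD, so smaller effects are shown as well. Alpha .025 is the Bonferroni worst case for Holm.

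| Effect | λ | Power at .05 | Power at .025 |
|---|---|---|---|
| f = .2 (SAP) | 24.8 | 99.6% | 99.0% |
| d = 0.5 (assumed) | 6.46 | 60.6% | 49.3% |
| d = 0.4 (assumed) | 4.13 | 41.8% | 31.1% |

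If both outcomes respond at 0.5 SD, Holm gives 54.9% per outcome at correlation 0 and 54.3% at .7.

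**The case against.** The strongest reply is that the aggregate is plainly the main test. The protocol's primary goal and the SAP's hypothesis concern plasma Aβ, and the power calculation was made for it. A direction of risk is given only for the aggregate: "Higher values on this composite measure are associated with greater risk". The ratio has no hypothesis, direction or power basis of its own. On that reading the rate is 5%. This shows what was probably intended, but nothing in the text places the ratio below the aggregate, although two lower tiers were available.

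Three technical cautions stand as qualifications:
- The 5% and 10% figures assume each ANOVA holds its nominal level. The SAP names no sphericity correction, and the simulation imposes compound symmetry.
- The F test has no direction, so false claims of benefit specifically would be rarer than the rates shown.
- What drives joint rejection is the correlation of within-person change between the two outcomes, which is unknown.

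The power figures also treat all 62 completers as analysable. SAP section 4 restricts the analysis to data of sufficient quality and gives no number for plasma.

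Finally, Holm is not the only remedy. Requiring both outcomes, or a documented single primary, would also close the gap.

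**Conclusion.** The concern holds. The plan permits two unadjusted .05 tests in the primary tier and does not define success. The inflation is conditional on the unwritten rule: above 5% and at most 10% if either outcome suffices, at most 5% if both are required, and 5% if only the aggregate counts. These figures assume that each test holds its nominal level; the position within the 5% to 10% range depends on an assumed correlation.

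The shared Aβ40 and Aβ42 measurements make some dependence likely. The ratio is not a function of the aggregate, however, so exactly 5% is not realistic under the either-suffices rule. The sample-size figure is not in error, and nothing here shows that any result is wrong. The gap concerns the trial's main inference and is cheap to close, so it should be fixed.

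**What to change.** State in the SAP, with a date, that Holm is applied across the two primary interaction tests: the smaller p-value against .025 and, if that is met, the larger against .05. Report both adjusted p-values. Holm controls the family-wise rate under any dependence and needs no ranking chosen after the fact.

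Label the rule as added after completion unless an earlier dated record shows it. Treat the aggregate as sole primary, or as first in a fixed sequence, only if a record made before results were seen supports that.

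The cost is a short text and two adjusted p-values, since both analyses are already specified. At the SAP's own effect size, the worst-case power loss is under one percentage point. At the assumed 0.4 to 0.5 SD it is about 11 points, and less if both outcomes respond.
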